**\*Non-Invasive Testing**

Device Name	Approval	Indication	
CardioSet	Investigational	measures lung volume using impedance technology	
ReDS unit	FDA	measures lung fluid content using radiofrequency waves	
Sphygmocor	FDA	measures arterial stiffness through a brachial cuff	
Bedside Ultrasound	FDA	performed of the heart, abdomen, kidney and diaphragm to assess left ventricular function, inferior vena cava dimensions and collapsibility, hepatic vein blood flow and portal vein flow and peripheral renal flow of the kidney	
Musculoskeletal Ultrasound	FDA	Utilizes muscle metabolic imaging derived from point of care musculoskeletal ultrasound for muscle mass, intramuscular glycogen content and intramuscular adipose tissue content	
InBody	FDA	Bioelectrical Impedance Spectroscopy: Segmental bioelectrical impedance spectroscopy (BIS) is another non-invasive way of assessing muscle quality assessment.	
VO2Master Pro	FDA	compact, mobile and wireless (bluetooth) breath-by-breath metabolic cart to assess the cardio-metabolic and cardio-respiratory capacity /effort during training (Rehab)	
PhysioFlow Hemodynamics	FDA	non-invasive hemodynamic monitor. It provides continuous, accurate, reproducible and sensitive measurements of cardiac output, stroke volume, systemic vascular resistance and left cardiac work index.	
Portalite and Moxy	Investigational	assessment of muscle- and brain mitochondrial function during cardiopulmonary exercise testing. The device is developed to measure concentration changes of oxyhemoglobin and deoxyhemoglobin with near infrared light.	
WHOOP strap 3.0	Investigational	measures heart rate variability and heart rate	
Questionnaire			
Dyspnea		7-point Likert scale and Visual Analog Scale	
EQ-5D-3L		Quality of Life	

Device Name	FDA Approval (Yes/No)	Indication
CardioSet	No	measures lung volume using impedance technology
ReDS unit	Yes	measures lung fluid content using radiofrequency waves
Sphygmocor	Yes	measures arterial stiffness through a brachial cuff
Bedside Ultrasound	Yes	performed of the heart, abdomen, kidney and diaphragm to assess left ventricular function, inferior vena cava dimensions and collapsibility, hepatic vein blood flow and portal vein flow and peripheral renal flow of the kidney
Musculoskeletal Ultrasound	Yes	Utilizes muscle metabolic imaging derived from point of care musculoskeletal ultrasound for muscle mass, intramuscular glycogen content and intramuscular adipose tissue content
InBody	Yes	Bioelectrical Impedance Spectroscopy: Segmental bioelectrical impedance spectroscopy (BIS) is another non-invasive way of assessing muscle quality assessment.
VO2Master Pro	No	compact, mobile and wireless (bluetooth) breath-by-breath metabolic cart to assess the cardio-metabolic and cardio-respiratory capacity /effort during training (Rehab)
PhysioFlow Hemodynamics	Yes	non-invasive hemodynamic monitor. It provides continuous, accurate, reproducible and sensitive measurements of cardiac output, stroke volume, systemic vascular resistance and left cardiac work index.
Portalite and Moxy	No	assessment of muscle- and brain mitochondrial function during cardiopulmonary exercise testing. The device is developed to measure concentration changes of oxyhemoglobin and deoxyhemoglobin with near infrared light.
WHOOP strap 3.0	No	measures heart rate variability and heart rate

### Testing procedures

**Blood volume analysis and scintigraphy:** Blood volume analysis will be performed using I131-radiolabelled albumin. The injection of the drug and associated blood draws will be completed in the nuclear lab. Patients will have a baseline blood sample drawn (4ml). Then, patients will be injected the radiolabeled albumin. After 12, 16 and 20 minutes we draw additional blood samples. The blood samples will be processed at the Duke nuclear laboratory using the Daxor analyzer or sent to Daxor Inc. for processing. If sent to Daxor for processing we will only share deidentified blood samples. Samples will be labelled with case number. We will provide patients age, gender and weight, which are needed for data calculation.

Following injection of the agent, the patient will also receive a **MUGA Scan** (Multiple Gated Acquisition scan) is a noninvasive tool for assessing the function of the heart. The **MUGA scan** produces a moving image of the beating heart but also allows to image the abdomen, and from this image several important features can be determined about the health of the cardiac ventricles and blood distribution.

Following injection of the technetium99, patients will be placed under a scintigraphy camera which will pick up the counts of radiation over the chest and abdomen. We will record resting counts over both compartments (chest /abdomen). Then patient will perform up to 5 min low resistance leg exercise while supine on a stepper placed at bed end. Counts will be recorded over both compartments during exercise.

Blood draws reported above will occur during resting recording. The exercise will occur after the 20 min blood draw is complete. Total duration of the study is anticipated to be 30 min.

The I-131 (Volumex) will either be administered by the nuclear medicine technician or [name]. Both have received training from the manufacturer.

**Nerve Block Procedure.** The unilateral, left-sided, temporal bilateral celiac plexus block will be performed by the interventional pain specialty team in the catheterization laboratory, with continuous hemodynamic monitoring similarly to our previously published experience. The celiac plexus block will be performed under fluoroscopic guidance in the posterior chest wall (vertebral space L1) to guarantee maximal safety (**Figure 2**). We will use a mix of 3 ml of lidocaine 1.55 with 1:10000 epinephrine, 10 ml of 0.5% ropivacaine and up to 1.5 U/kg of BTX Type A. Lidocaine with epinephrine is used for procedural

safety to exclude intravascular injection. In the present study we will start at a lower dose of the BTX (dose finding). We will plan to increase dose or decrease per Kg unit doses for Botox based on 4 week assessment.

The dosing up titration scheme (Scenario 1) is as following:

1. The 1st and 2nd subject receiving the block splanchnic procedure - 75Units of Botox, (not more than 1.5 Units/kg) follow up at 2 weeks with CPX and 4 weeks with invasive CPX and 8 weeks with CPX
2. The 3rd and 4th subject receiving the block splanchnic procedure - if prior dose tolerated, no safety issues at 4 weeks than proceed with dose increase to: 100Units of Botox, (not more than 1.5Units/kg) follow up at 2 weeks with CPX and 4 weeks with invasive CPX and 8 weeks with CPX
3. The 5th and 6th subject receiving the block splanchnic procedure - Scenario 1: if prior dose tolerated, no safety issue and satisfactory efficacy at 4 weeks than patient 5/6 will get injection of 100Units of Botox again (not more than 1.5Units/kg) with follow up at 2 weeks with CPX and 4 weeks with invasive CPX and 8 weeks with CPX Satisfactory efficacy is defined as >25% reduction with exercise wedge pressure  
Scenario 2: if prior dose tolerated, no safety issue and efficacy not satisfactory at 4 weeks than patient 5/6 will get injection of 125Units of Botox (not more than 1.5Units/kg) with follow up at 2 weeks with CPX and 4 weeks with invasive CPX and 8 weeks with CPX.

Dose down titration scheme is as following: If BP is too low (newly <90mmHg, independent of heart failure medication changes done clinically) or patient report orthostatic symptoms we will return for the next patient to the preceding lower Botox dose. If symptoms of orthostasis or hypotension are experienced already at the lowest dose we will drop the injection dose to 50 Units (not more than 1.5U/kg) . The effects of ropivacaine are expected to occur as early as 15 minutes and last for 24h. The acute effects will serve as confirmation of procedural success and provide reassurance that BTX was injected in the right location. BTX is a neurotoxin that blocks cholinergic neurotransmission and offers temporary autonomic modulation via ganglionic block. The peak pharmacological properties of BTX are expected at 2 weeks post injection. The estimated duration of BTX effect is up to 4-6 months.

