## Design & Procedures

- Describe the study, providing detail regarding the study intervention (drug, device, physical procedures, manipulation of the subject or the subject's environment, etc.). Discuss justifications for placebo control, discontinuation or delay of standard therapies, and washout periods if applicable. Identify procedures, tests and interventions performed exclusively for research purposes or more frequently than standard of care. Include alternative therapies, concurrent therapies discontinued per protocol, risk benefit ratio, and use of tissue/specimens. Discuss monitoring during washout periods if applicable. Include brief description of follow-up, if any.

**Study design.** The present study will be a prospective open-label pilot study to help establish feasibility, safety and enable dose finding for BTX. The schedule of events is presented in **Figure 3**. Following a baseline invasive (right heart catheterization) cardiopulmonary exercise testing (CPX) patients will undergo unilateral celiac plexus block (**Figures 2 and 4**), followed by repeat hemodynamic testing in the following 90 minutes. Repeat CPX (with and without hemodynamic testing) will occur at 2, 4, 8 weeks. A 12 month phone call to investigate vital status, HF hospitalizations will conclude the study. Functional testing at baseline and follow up will be supplemented by a series of minimally invasive and non-invasive measures of static and dynamic blood volume distribution (radionuclear plethysmography, bioelectrance, hepatic vein ultrasound), congestion parameters (biomarkers, BVA), autonomic nervous tone (catecholamines,

baroreflex, and heart rate variability) and symptom questionnaires (Likert and Visual Analog scale). Given high volume of patients and right heart catheterizations (>1,000 per year) and our experience with enrolling patients in the preliminary studies, we anticipate to complete recruitment within 2 years.

Figure 2. Splanchnic Nerve Block Procedure (A) and Prior Data of Nerve Blockade in Acute (B) and Chronic Heart Failure (C). \* indicates p<0.05

[figure not shown]

Figure 3. Study Flow

[figure not shown]

Figure 4. Study set-up: Invasive hemodynamic testing

[figure not shown]

Table 1: Schedule of events (CS, clinical study; SOC, standard of care/clinical)

Required Assessment	Pre-Procedure (Day 1)	Baseline (Intra-Procedure)	Block	Post-Block Procedure	48 Hour	Week 1	Week 2	Week 4	Week 8	Month 6	Month 12

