Vitals (BP, HR, RR, SpO 2 , weight)	X (CS)			X(CS)		X(CS)	X(CS)	X(CS)			
Orthostatic vitals	X(CS)			X(CS)		X(CS)	X (CS)	X (CS)			
Non-Invasive Testing*	X(CS)			X(CS)		X(CS)	X (CS)	X (CS)			
Pregnancy test	X (SOC)										
Labs: BMP (SOC), pro-BNP (CS), CA-125 (CS), urine sodium (CS),	X (CS /SOC)			X (CS /SOC)		X (CS /SOC)	X (CS /SOC)	X (CS /SOC)			
Labs Renin, Angiotensin II, Vasopressin, Plasma Catecholamines	X (CS)			X (CS)		X (CS)	X (CS)	X (CS)			
				X(CS)	X(CS)				X(CS)	X(CS)	

Dyspnea and EQ-5D-3L Questionnaires	X (CS)		X(CS)		X(CS)	X (CS)	X(CS)		
Six minute walk test	X (CS)		X(CS)		X(CS)	X (CS)	X(CS)		
Blood volume - Daxor	X (CS)					X (CS)			
Heart rate variability	X (CS)	X (CS)	X (CS)		X (CS)	X (CS)	X (CS)		
Right Heart Cath (RHC)		X (CS, SOC)				X (CS)			
Scintigraphy	X (CS)					X (CS)			
Invasive CPX (peak VO2)		X (CS)				X (CS)			
CPX (peak VO2)					X (CS)		X (CS)		
Echocardiogram		X (CS)	X (CS)		X (CS)	X (CS)	X (CS)		
Renal ultrasound (to be done by [name])	X (CS)		X (CS)		X (CS)	X(CS)	X (CS)		
Splanchnic nerve block			X (CS)						
Phone Call				X (CS)	X (CS)			X (CS)	X (CS)

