  6. Heart Rate Variability: The WHOOP strap 3.0 will measure heart rate and heart rate variability and will be worn for approximately one hour.
3. 6 minute walk test to measure your exercise capacity and endurance.
4. Questionnaires about the subject's feeling about their shortness of breath and breathing at rest
5. Cardiopulmonary (CPX) Testing: Exercise testing with the subject using an upright bike. The subject will exercise at their maximum effort. The subject will be monitored for exercise intolerance, shortness of breath, or pain in the chest. The subject will wear a face mask to measure oxygen intake and carbon dioxide output.
6. MUGA Scan: non-invasive imaging method to evaluate the function of your heart. This scan will help determine more information about the health of the subject's cardiac ventricles and blood distribution.

Laboratory Tests:

1. Blood Volume Analysis: Administration of a small amount of plasma protein, albumin, containing a small amount of radioactive iodine (injected through the PIV). The radioactive iodine labeled albumin

protein (blood volume solution) will be administered through the PIV line. Blood samples will be withdrawn before administration of the blood volume solution and 12, 16 and 20 minutes after administration. The blood samples will be processed at the Duke Nuclear Laboratory using the Daxor Analyzer for further processing

2. Biomarkers: Blood samples will be taken before the procedure and after the procedure for analysis of NT pro-BNP (indication of worsening heart failure) and CA-125 (indication of inflammation).
3. Autonomic Nervous System regulators: Blood samples will be taken in the catheterization lab before and after the splanchnic block. The samples will be processed and sent out to labs that specialize in analyzing these samples for hormones angiotensin II, vasopressin, catecholamines, and metanephrines.

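### The block mix contains epinephrine, so same-day epinephrine, metanephrine or total-catecholamine changes are biased upward by study drug and should be listed, not tested (minor)

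*Combined protocol and SAP*

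**What the plan says.** All references are to the combined protocol and SAP.

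- **Injection.** The Nerve Block Procedure paragraph under Testing procedures specifies "We will use a mix of 3 ml of lidocaine 1.55 with 1:10000 epinephrine, 10 ml of 0.5% ropivacaine", plus botulinum toxin (BTX). It explains that the lidocaine with epinephrine is there to rule out an intravascular injection. Study Interventions, invasive test 1, describes the solution as ropivacaine and Botox only and mentions neither lidocaine nor epinephrine.
- **Sampling.** Study Interventions, laboratory test 3, states "Blood samples will be taken in the catheterization lab before and after the splanchnic block", for "hormones angiotensin II, vasopressin, catecholamines, and metanephrines". Table 1 has a row "Labs Renin, Angiotensin II, Vasopressin, Plasma Catecholamines". As extracted, it is marked before the procedure, after the block and at three later visits.
- **Purpose.** The Study design paragraph lists these assays among the measures of "autonomic nervous tone (catecholamines" and other indices.
- **Design.** "The present study will be a prospective open-label pilot study to help establish feasibility, safety and enable dose finding for BTX". No control or sham arm is described. The order is "Following a baseline invasive (right heart catheterization) cardiopulmonary exercise testing (CPX) patients will undergo unilateral celiac plexus block", "followed by repeat hemodynamic testing in the following 90 minutes".
- **Analysis.** Data Analysis & Statistical Considerations applies t-tests to continuous outcomes, with a two-sided 0.05 level for change from before to after the procedure. It names no catecholamine fraction and does not mention the injected epinephrine.

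**The concern.** A block of sympathetic outflow would be expected to lower circulating catecholamines, if it moves them at all. The injection itself supplies a catecholamine, and the same class of substance is assayed in the same session as a marker of autonomic tone. The drug contribution and the block effect therefore act in opposite directions on epinephrine, metanephrine and any total. Without a comparison group, a stated draw time or a restriction on the fractions analysed, the before/after difference cannot be divided between them.

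Two misreadings become possible. A real same-day fall could be hidden or reversed, or a rise caused by the drug could be reported as a significant effect of the block. What is at stake is one exploratory mechanism readout. Catecholamines appear in none of the three primary objectives, no secondary objectives are stated, and neither the up-titration nor the down-titration rule uses them.

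**Working it through.** **Dose.** The plan states no epinephrine mass, so there is no figure of its own to reproduce. The inputs are the 3 ml volume and the 1:10000 strength from Nerve Block Procedure. A 1:r solution is 1 g in r ml, so dose = 3 ml × (1,000,000 micrograms / r ml).

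| Strength | Micrograms/ml | Dose in 3 ml |
|---|---|---|
| 1:10,000 (as written) | 100 | 300 micrograms |
| 1:100,000 (assumed alternative) | 10 | 30 micrograms |
| 1:200,000 (assumed alternative) | 5 | 15 micrograms |

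The alternatives are shown because the lidocaine strength in the same sentence (1.55, no unit) looks garbled, so the epinephrine strength may be a slip too. The dose is above zero in every row.

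**Direction.** For a same-day analyte, observed change = block effect + drug contribution + other change. For epinephrine, metanephrine and a catecholamine total, the direct drug contribution is zero or positive. For norepinephrine and normetanephrine there is no direct contribution. An indirect one cannot be excluded, and its sign is not known.

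**Size.** This cannot be computed, because the documents give no absorption, no clearance and no draw time. The following is an illustration only. Assume full absorption over 30 to 90 minutes and clearance of 2 to 10 L/min. Mean added concentration during absorption = dose / (time × clearance).

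- 300 micrograms: 300/(90 × 10) = 0.33 micrograms/L to 300/(30 × 2) = 5 micrograms/L, or about 330 to 5,000 pg/ml.
- 30 micrograms: about 33 to 500 pg/ml.
- 15 micrograms: about 17 to 250 pg/ml.

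Within one dose the range is 15-fold. It is an average during absorption, not the level at an unstated draw time, so it does not estimate the bias.

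**Behaviour of the test.** A contribution shared by all subjects does not average out. In a paired t-test (the plan says only t-test), the smallest mean change declared significant is t(0.975, n−1)/√n, in SDs of the within-patient differences.

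- n = 6: 2.571/2.449 = 1.05
- n = 10: 2.262/3.162 = 0.72
- n = 20: 2.093/4.472 = 0.47

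The plan states no sample size; six is the number of subjects in the dosing scheme. These thresholds hold for any paired t-test and are not evidence about epinephrine. They show only that adding subjects makes a shared shift easier to declare significant.

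**The case against.** The strongest reply has four parts.

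1. **The plan never names epinephrine or a total as an analyte.** This is correct. It says catecholamines and metanephrines, without fractions, and the analysis section is generic. If only norepinephrine and normetanephrine were reported, the direct problem would disappear. But nothing in the plan makes that restriction, and stating it is the core of the fix.
2. **It is not certain that epinephrine is given, or at what strength.** Study Interventions omits it, and 1:10000 may be an error. Both points stand as uncertainty. Nerve Block Procedure is nevertheless explicit and gives a reason for using it, and a weaker solution shrinks the contribution without removing it.
3. **The drug may have largely cleared by the draw.** That is possible, but the plan sets no draw time on which to rely.
4. **The stakes are low.** This stands. The study is an open-label pilot, BTX is expected to peak at two weeks, and the assay drives no decision. It is also fair that Table 1, as extracted, already places the baseline sample in a column ahead of the baseline invasive exercise test, so that ordering needs no change.

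A reader might infer more: that the same-day result will be reversed or falsely significant, that heart rate variability, baroreflex or the later-visit samples are also invalid, or that the acute check of procedural success is undermined. The documents support none of these. The size of the shift is unknown, effects on the other autonomic measures could only be indirect, nothing shows carry-over to later visits, and the passage on confirming procedural success does not mention catecholamines.

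**Conclusion.** The point holds, as a minor one. If epinephrine is injected as Nerve Block Procedure describes, any same-day epinephrine, metanephrine or total-catecholamine change carries a direct upward contribution from study drug that this single-arm design cannot separate from the block. The dose is 300 micrograms as written, or 30 or 15 at the two assumed weaker strengths. The resulting shift in the blood sample is not computable from the documents.

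The conclusion rests on two readings: that the unrestricted assay wording covers these fractions, and that the generic before/after test would be applied to them. It is confined to the same-day comparison of an exploratory outcome.

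**What to change.** 1. **Study Interventions, laboratory test 3.** Add: *Norepinephrine and normetanephrine, reported separately, are the same-day readout; indirect effects of the injected epinephrine on them cannot be excluded. Same-day post-block epinephrine, metanephrine and total catecholamines are listed but not tested. They are compared with baseline only at the later Table 1 visits where they are assayed.*
2. **Data Analysis & Statistical Considerations.** Add: *No same-day before/after test is done on epinephrine, metanephrine or total catecholamines.*
3. **Sampling.** Record the clock times of the injection and of each draw. Take the post-block sample at rest, before any repeat exercise, without delaying the hemodynamic testing, which serves the primary objectives.
4. **Drug description.** Confirm or correct the epinephrine strength in Nerve Block Procedure, and make invasive test 1 in Study Interventions list the same drugs.

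**Cost.** Wording in these sections and three clock-time fields on the case report form, with no added patients, visits or blood draws. The same-day epinephrine and metanephrine test is given up. The Table 1 row names plasma catecholamines but not metanephrines, so a later-visit metanephrine comparison, if wanted, means adding that assay to samples already drawn.

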### Data & Safety Monitoring

- Summarize safety concerns, and describe the methods to monitor research subjects and their data to ensure their safety, including who will monitor the data, and the frequency of such monitoring. If a data monitoring committee will be used, describe its operation, including stopping rules and frequency of review, and if it is independent of the sponsor (per 45 CFR 46.111(a) (6)).

Due to the experimental nature of this intervention, data will be recorded after each subject completes the intervention for signs of unintended negative effects. These include hypotension, worsening renal function, or clinical deterioration. Additionally, subject's electronic medical data will be screened for any traumatic complications from the nerve block at 2 weeks, and 6 months post-procedure.

Unanticipated severe adverse events will be reported to the IRB per IRB policy.

In accordance with federal regulations the PI will monitor for review, and promptly report to the IRB, appropriate institutional officials, sponsor, coordinating center and the appropriate regulatory agency head, all unanticipated problems involving risks to subjects or others that occur in the course of a subject's participation in research study, in accordance with (45 CFR 46.103(b)(5)(i) and 21 CFR 56.108(b)(1)), all AE reports will be reported per the DUHS IRB policies.

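### No interval is set between the two subjects at a new Botox dose; holding the second until the first's 2-week visit is a cheap safety improvement

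*Combined protocol and SAP*

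**What the plan says.** The Nerve Block Procedure text under Testing procedures sets out three pairs.

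- Subjects 1 and 2: "The 1st and 2nd subject receiving the block splanchnic procedure - 75Units of Botox".
- Subjects 3 and 4: 100 units, if the prior dose was tolerated without safety issues at 4 weeks.
- Subjects 5 and 6: in Scenario 1 (satisfactory efficacy), "than patient 5/6 will get injection of 100Units of Botox again"; in Scenario 2 (efficacy not satisfactory), 125 units.

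Every dose is capped at 1.5 units/kg. On the timing of dose changes in either direction, the section says "We will plan to increase dose or decrease per Kg unit doses for Botox based on 4 week assessment".

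The down-titration paragraph that follows has two triggers, a new blood pressure below 90 mmHg or reported orthostatic symptoms. When either occurs, "we will return for the next patient to the preceding lower Botox dose"; from the lowest dose the step is to 50 units. On pharmacology it states "The peak pharmacological properties of BTX are expected at 2 weeks post injection" and "The estimated duration of BTX effect is up to 4-6 months". The ropivacaine in the same injection is expected to act from about 15 minutes and to last 24 hours.

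Data & Safety Monitoring adds that "data will be recorded after each subject completes the intervention for signs of unintended negative effects", and that electronic medical data will be "screened for any traumatic complications from the nerve block at 2 weeks, and 6 months post-procedure". Risk/Benefit Assessment provides several hours of monitoring after the block and a re-examination at 2 weeks. Table 1 lists two early phone contacts, apparently at 48 hours and Week 1, although its column alignment is broken.

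**The concern.** The between-pair check is explicit, but nothing visible says how long to wait between the first and second subject of a pair. Subjects 2 and 4, and subject 6 in Scenario 2, are each the second person at a dose new to the study. Each could be injected before the first person at that dose reaches the expected peak of effect.

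The step-down rule acts patient by patient, so it can protect the second subject only if the trigger is seen before that subject's injection. If it is seen afterwards, the second subject already carries a dose that the rule would have lowered, with an effect estimated to last months. Entry requires systolic pressure above 100 mmHg and the trigger is below 90 mmHg, so the margin can be little more than 10 mmHg.

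**Working it through.** The plan states no sample size and no operating characteristic for the dosing scheme, so there is no figure of its own to reproduce.

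**Inputs from the plan:** three pairs; a 4-week check between pairs; peak at 2 weeks; 2-year recruitment (104 weeks); doses of 50, 75, 100 and 125 units; cap of 1.5 units/kg.

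**Assumed inputs:** total N of 6 to 20 (the scheme names six subjects) and random (Poisson) arrivals at r = N/104 per week.

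**1. Earliest calendar.** Counting the 4 weeks from the second subject of each pair, the earliest injection weeks are:

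- As written: 0, 0, 4, 4, 8, 8.
- With a 2-week hold at each new dose, Scenario 1: 0, 2, 6, 8, 12, 12. The last injection moves by 4 weeks; 4/104 = 3.8%.
- With the same hold, Scenario 2: 0, 2, 6, 8, 12, 14. It moves by 6 weeks; 6/104 = 5.8%.

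**2. Chance of a gap under 2 weeks, per pair:** 1 − exp(−2N/104).

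- N = 6: 1 − exp(−0.115) = 10.9%
- N = 10: 1 − exp(−0.192) = 17.5%
- N = 20: 1 − exp(−0.385) = 31.9%

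**3. Expected delay from the hold, per pair:** 2 − (1 − exp(−2r))/r weeks. This gives 0.11 (N = 6), 0.18 (N = 10) and 0.34 (N = 20).

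**4. What the hold could prevent.** It helps only when the first subject's trigger falls after the second injection and by week 2. As an illustration, suppose a trigger arises at some point in weeks 0 to 2 with uniform onset (an assumption). The chance that it falls in that window is the expected delay divided by 2: 0.111/2 = 5.5% after rounding down from 5.55% (N = 6), or 0.340/2 = 17.0% (N = 20). Multiplying by an assumed trigger rate of 10% to 50% gives 0.6% to 2.8% per pair (N = 6) or 1.7% to 8.5% (N = 20). The plan supplies neither the rate nor the onset pattern.

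**5. Avoidable excess dose at weight w:** min(high, 1.5w) − min(low, 1.5w).

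| Comparison | Zero at or below | Full 25 units from |
|---|---|---|
| 75 vs 50 units | 33.3 kg | 50 kg |
| 100 vs 75 units | 50 kg | 66.7 kg |
| 125 vs 100 units | 66.7 kg | 83.3 kg |

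**6. Existing safeguards against the 2-week peak.** Same-day monitoring falls within the ropivacaine window, nearly two weeks before the expected Botox peak. The early calls also precede the peak; they can pick up symptoms but cannot be assumed to measure blood pressure. Recording after each subject delays no injection. The dated 2-week chart screen is for traumatic complications. The step-down rule has no waiting time.

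**The case against.** The strongest case against is that the plan already works patient by patient. Step-down applies to the next patient rather than the next pair, and data are recorded after each subject, which most naturally suggests sequential dosing with review. The same-day ropivacaine block also gives an early reading of block-related hypotension, and Risk/Benefit Assessment reports 28 lidocaine/ropivacaine cases without acute or chronic complications. At the likely accrual rate most gaps would exceed 2 weeks anyway. The dose difference at issue is at most 25 units, and nothing in the plan shows that 25 units changes risk.

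Most of this stands and is why the gain is modest. It does not remove the gap: sequential dosing without a stated wait still allows a second injection before the peak, and an uneventful day under ropivacaine does not exclude a delayed Botox effect. Background & Significance cites only one case of Botox at this target, reported as safe. Its 48-hour side-effect window comes from surgical or alcohol blockade in patients without heart failure.

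A reader might also infer that a triggering dose should bar the following pair from escalating. The gap within pairs does not support that. It would be a new escalation rule, and because any reported orthostatic symptom is a trigger, one transient report could curtail the dose finding.

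**Conclusion.** The point holds as a cheap safety improvement, worth making but small. Two subjects of the six named are exposed to the gap in Scenario 1 and three in Scenario 2. The 11% to 32% is the chance of a short gap per pair, conditional on the assumed N and random arrivals. The chance of preventing a higher dose is smaller and cannot be fixed from the plan.

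Three stronger readings are not supported.

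- A reader might infer an error or contradiction. There is none; the visible text is silent on the interval, and Figure 3 might address it.
- A reader might take the short-gap chance as a chance of harm. A trigger in the right window is also needed, and the plan does not say when Botox-related hypotension would appear. That it follows the 2-week peak is an assumption.
- A reader might multiply the short-gap chance by the rate of any trigger after the second injection. At an assumed 10% to 50% this gives 1.1% to 5.5% (N = 6) or 3.2% to 16.0% (N = 20). It overstates the benefit, because it includes triggers after week 2 that the hold would not catch.

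**What to change.** Add to the up-titration scheme: at each Botox dose not yet used in this study, the second subject is injected only after the first subject's 2-week visit (blood pressure, orthostatic vitals, symptoms, adverse events) has been reviewed. If a down-titration trigger has occurred, the second subject receives the lower dose under the existing step-down rule, not more than 1.5 units/kg. Leave the 4-week between-pair check and the escalation criteria as they are. Subject 6 in Scenario 1 needs no hold, because 100 units will already have been used.

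The visit already exists, so the cost is wording plus at most 2 weeks per new-dose pair: the 4 or 6 weeks shown above. Time is lost only when the next case arrives within 2 weeks. Because subjects come from elective right heart catheterizations, a case falling inside a hold may occasionally be missed, and a step-down may split a pair across two doses. A trigger first seen after week 2 would still come too late for a second subject already injected.
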